# Economic considerations

The final evaluation of the feasibility of the intervention will take into account economic considerations. We will determine whether a cost-effectiveness, cost- consequences or cost-benefit study will be most appropriate. In our planning, we have proposed a cost-utility study using the EQ-5D as the preferred approach. We will use the standard methods for establishing cost-effectiveness against a societal threshold based upon the reference case method suggested by NICE. In keeping with common practice, we will use a societal perspective for the cost-utility analysis but will also consider the appropriateness of adopting a health and social care perspective.

We will use a resource use approach to costing, and we will build a cost model using price weights derived from national sources such as PSSRU. The main outcome measure for the economic analysis will be the EQ-5D, but a cost-effectiveness analysis will also be undertaken using the primary clinical outcome measure chosen after feasibility study. We will collect resource use and outcome data using a self-reporting questionnaire. This data will be used to build an economic model, which will inform the cost-utility and cost-benefit analysis. The model type and structure will be determined during the feasibility study. For example, the EQ5D measurements will enable us to model QALY and will inform a future Markov model for economic impact of the intervention to other NHS services and quality of life.

We will test the feasibility of a full-scale economic evaluation using the following criteria: (i) Can cost and outcome data be successfully collected? (ii) Can a viable model be built that produces robust data for an economic study? (iii) Can an appropriate form of evaluation study be performed using robust methods? (iv) Does the economic modelling align with the objectives of the clinical study? (v) Can results be presented in a way useful to NHS decision-makers and can accompanying uncertainty analysis be performed?

Our main economic analysis is designed to provide NHS decision-makers with the information they need to assist commissioning. In addition, we will also build a cost/profit model for pharmacy providers, as a means of demonstrating the net benefits of providing the services described. In this model, we will take a pharmacy

perspective and will consider the costs of hiring additional staff and running the service. We will then perform a sensitivity analysis that estimates profitability for a range of cost and NHS fee scenarios. We will present the results from this analysis alongside the main economic modelling.

**H. Feasibility of a future cluster randomised controlled trial -** A final analysis and evaluation will be conducted by the research to team to scope the requirements of a future cluster randomised controlled trial. We are working with LinCTU who will facilitate collection of data and analysis. A detailed list of criteria for progression to full trial, with an indication of red/amber/green specifications has been developed (See Appendix 1).

#### Engagement and dissemination

To inform communication, the key findings for acceptability, feasibility, potential effectiveness, costeffectiveness and impact on pharmacy business will be refined put into a table of activities and messages for LinCTU. The co-investigator GL is deputy director of this CTU. Their involvement will consist of setting up all of the progression criteria and associated data collection on CASTOR trials software.

This will ensure full GDPR compliance and that all data is stored in secure cloud access in the UK. They will assist with participant information sheets, consent forms and applying for ethical approval. The CASTOR software will allow data recording templates to be available to the pharmacies online so that they can enter the data at the time of the consultation, and the data will go directly to the database. It also allows the research team to have access to live and comprehensive data. They will conduct all randomisation and statistics and provide data monitoring and study support. GL and the CTU will play a significant role in the final evaluation of feasibility.

A Study Steering Group and PPIE panel have been established. There will be on-going engagement with these groups throughout the study, with regular meetings. A database of partners and interested people/ parties will be held and updated throughout, with updates sent to those on the database. Participants will have the option to receive updates on the project. This will be accompanied by active engagement and dissemination with partners, for example update presentations at the Lincolnshire Suicide Prevention Steering Group. There will be a project website and social media will be used.

In terms of formal reporting, the qualitative findings will be reported for publication using the COREQ template, and the details of the intervention using TIDieR. The study protocol will be submitted for the publication as well as the final outcomes (co-development publication and feasibility publication). A detailed report of the completed project produced for the NIHR library will be published and freely available on our website and NIHR website.

# RANDOMISATION AND BLINDING

A sampling framework will be used to recruit three pharmacies per the following category with a spread across different socio-economic areas (based on deprivation index from Office for National Statistics):

- Rural small pharmacy / rural large pharmacy
- Non-rural small pharmacy / non-rural large pharmacy

Randomisation will then be conducted by the CTU, to give 2 pharmacies from each of the four categories as interventions (total of 8), and 1 pharmacy from each of the four categories as a control (total of 4).

Because of the nature of the intervention and promotion, pharmacy staff, participants and researcher working with pharmacies will not be blinded.

#### STUDY REGIMEN

#### SCHEDULE OF PROCEDURES

#### Data collection measures and time points for Phase 2: Feasibility Randomised Control Trial

Procedures	Screening	Intervention delivery	Post intervention				
Pharmacies allocated to intervention							
Service users							
Service user assessment for eligibility		Х					
Informed consent		X					
Demographics & health Status		X					
Satisfaction		X					
Pharmacy staff							
Recruitment, informed consent and training	x						
Service delivery		X					
Usage and referral		X					
Business data		X					
Focus Group at UoL or online			x				
Summary workshop at UoL			x				
Pharmacies allocated to	control	I	I				
Number of enquiries and referrals		X					
Business data		X					

#### WITHDRAWAL

Participants may be withdrawn from the study either at their own request or at the discretion of the Investigator. The participants will be made aware that this will not affect their future care. Participants will be made aware (via the information sheet and consent form) that should they withdraw, the data collected to date may not be erased in accordance with the University's Research Privacy Notice and information given in the Participant Information Sheet and may still be used in the final analysis.

# ETHICAL AND REGULATORY CONSIDERATIONS

# ASSESSMENT AND MANAGEMENT OF RISK

#### Sensitive nature of this research

This project includes clients from vulnerable groups who are survivors, patients or people with an interest in helping people experiencing domestic violence / suicidal ideation. As such, the research will need to be accomplished with great skill and sensitivity. At all times we will use listening and non-judgemental techniques to create an open yet confidential safe space for people to discuss their views.

#### Experience of research leads and research team

The study will be carried out by an experienced research team with appropriate clinical, research expertise and experience with working with vulnerable groups. The Chief Investigator ([name]) is the CI and co-lead for this study with [name]. Both are experienced pharmacists, academics and have successfully delivered projects that have involved co-production, evaluation and working with marginalised and vulnerable groups.

Specifically, [name] has expertise in psychological interventions, engagement projects on domestic abuse and child safeguarding, and pharmacy education. She also holds counselling qualifications. [name] is an experienced mixed-methods pharmacy practice researcher who has expertise in co-production and evaluation methods and working with marginalised groups including children and young people who have self-harmed. He has also served a full term as an expert member of the NRES Nottingham 2 Research Ethics Committee (2012-17). The wider research team is also highly experienced with expertise in psychological interventions, participatory research and health intervention economic evaluations.

#### Phase 1:

# 1. Interview with professional stakeholders

These interviews are not expected to raise any significant ethical issues, cause distress or make the participant upset. This is because they will be centred on service development issues i.e. help us to map referral pathways, advise on appropriate content of the pharmacy's education and training resources and other procedural aspects of the service (e.g. advice on clinical record keeping).

# 2. Lay focus groups

Two lay focus groups will be held. One for lay people with experience of domestic abuse, and one for lay people with experience of suicidal ideation. These groups will explore the lived experience and barriers to access for support for each issue.

All participants will receive an information sheet at least 24 hours before the focus group, be fully informed beforehand about the topic to be discussed and be informed that participation is entirely voluntary and that they can withdraw at any time.

Before the workshop, will also inform everyone that the focus group will be run under 'Chatham House Rules' to ensure people are able to express themselves without fear of disclosure of what is said directly or indirectly by any participant. These are potentially emotive topics and there is possibility for participants to become upset. We will discuss issues relating to domestic abuse / suicidal ideation in a sensitive way and seek to frame the discussion positively i.e., focus on the opportunity for the research team to learn and for this to be then applied to provide better support to individuals.

We are aware of potential gender-power issues and so JS will lead on discussions relating to domestic abuse. During the focus group, should any participant appear to become upset during the workshop, there will be sufficient facilitators to be able to accommodate their needs. Should they wish, the participant will be invited to leave the discussion / room as long as is needed. They may either withdraw or come back to the group depending on their preferences. JS has training in counselling and has experience of research on sensitive issues. [name] is also an experienced pharmacist-academic who has run co-production workshops with vulnerable people before.

All participants will be invited to carry forward with the project, in to the co-development workshops if they should wish.

# 3. Co-development workshops

All participants will receive an information sheet and be informed about the nature of the workshop at least 24 hours beforehand. Written informed consent will be received before the workshop. Like the focus groups, we will inform everyone that the workshop will be run under the Chatham House Rules and use the same measures as the focus groups should any participant appear to become upset or want to leave the discussion. We will use a mix of small group work, and larger group discussion with a facilitator mingling between groups to ensure that everybody has the chance to speak. We will encourage participants to respect the views and opinions of others. As such, it is not anticipated that any participants will feel marginalised during the workshops.

# Phase 2: Feasibility study

# 1. Service Delivery

# A. Potential burden on pharmacists and pharmacy staff

Once permission is granted from the Head Office / Owner, the pharmacy staff will be invited to take part. It will be made clear to all pharmacy teams what will be involved. They will receive at least 24 hours to decide whether or not to take part. It will be made clear that their decision regarding participation in the study will be entirely voluntary and that any staff member can withdraw from delivering the service and study at any time should they wish to do so. As employees they will be assured that not taking part will not disadvantage them in terms of their appraisal / salaries etc.

If they agree, pharmacy staff will receive training and support to fully prepare them to deliver the service. Training will include how to manage and respond to requests for help, study procedures and training on the principles of GCP. The pharmacy will be randomly allocated and receive support costs according to whether they deliver the service / or act as controls. At the end of the study, recruited pharmacy staff will take part in a focus group discussion and summary workshop.

The pharmacy staff will receive monthly support visits from the researcher, and can contact the researcher in-between visits for additional support or advice.

# B. Delivering the pharmacy response service delivery: disclosure of sensitive information

All pharmacy staff will be trained on the ethical issues around the disclosure of sensitive information. We expect there to be a range of service-user needs. The training will involve roleplay and scenarios to prepare pharmacy staff for eventualities including what to do if the service-user is in immediate danger. These are complex issues that the feasibility study will seek to explore and understand how well pharmacy staff can cope with managing such situations.

# C. Collecting data from service-users at the time of accessing the service

We recognise that clients (service-users) are likely to be distressed at the time of accessing the service. We aim to achieve an ethical balance between gathering sufficient service data for us to be able to assess the feasibility of the service, and not over-burdening them at a difficult time.

Including data and the views of clients is important, to ensure that the final intervention that will be produced at the end of feasibility is appropriate and relevant to this client group. Excluding such individuals could introduce bias as the sample would not be representative of the population and it may reduce the utility of the research findings. Furthermore, it is argued that vulnerable groups should be protected through research, rather than from research.

However, our priority is the welfare of the client. We have taken a number of steps to safeguard the clients in the research process.

The pharmacy staff will be trained to ensure the wellbeing and safety of service-users accessing the service will be the paramount consideration. There will be a clear assessment of risk before the service-user is invited. We anticipate that most requests for the service will be for lower-level support. (See table 4) i.e. Levels 1 (Signs of concern) or Level 2 (Active concern). We do not anticipate many will be at the highest level (Level 3 - Immediate danger). Pharmacy staff will be trained to invite potential participant who are categorised at Level 1 & 2. For those in Level 3, pharmacy staff will be trained to manage these case with discretion, urgency and compassion.

We have divided the data to be collected in the consultation in to two parts. Part A contains the data necessary to be able to effectively triage the client and refer appropriately. Part B consists of supplementary data for the purposes of evaluating the feasibility of the study. Clients will be invited to consent to both parts, but if the client is unwilling to consent to Part B, they will still be offered the service with the collection of Part A data only. Similarly, the pharmacy staff may use their judgement in cases of considerable distress or urgency to omit Part B and deliver Part A only, so as to respond swiftly and effectively to their needs.

To ensure we collect data about service use and acceptability, we will seek to collect basic demographic data and brief views on service acceptability when service-users access the service. The pharmacy staff will explain this is a trial service and invite the individual to offer their views. The data will be collected during the consultation. The consultation will take place in a private consultation area to ensure privacy. Potential participants will be informed that all data collected for the research is anonymised.

Consent (for Part A and Part B as appropriate) will be obtained at the time of contact. Clients will be provided with a Participant Information Sheet and Participant Consent Form. Because of the nature of the service, prior consent is not possible and there is a limited time frame for the initiation of the intervention being tested. We recognise that the usual 24 hour notice period will therefore not apply.

The pharmacy staff will go through the participant information sheet with the service user. They will be invited to take this away if they choose. Information sheets will be made available in the additional languages of Polish, Lithuanian, Hindi and Urdu.

It will be explained that offering study information is entirely voluntary and declining to provide this additional information will not affect the care they receive in any way. Pharmacy staff will check for understanding and provide the opportunity for potential participants to ask questions and withdraw their consent at any time.

In terms of data collection, all of the client data is collected in the consultation. We did not feel that contacting participants after the service to collect follow up data would be appropriate (risk of breach of confidentiality / potential to raise suspicions with abusive partners).

The study data collected will not be extensive. It will comprise of simple demographic data, brief views about acceptability, satisfaction and health status. We already have extensive PPIE input in the design of these procedures. We will further test these as part of Phase 1 (co-development) of the study where we anticipate there will be further refinement of the triage process, referral and data collection tools.

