#### STUDY MANAGEMENT COMMITTEES

Lincoln Clinical Trials Unit (LinCTU). The co-investigator GL is deputy-director of the CTU. The CTU's involvement will consist of setting up all of the progression criteria and associated data collection on CASTOR trials software. The CASTOR software will allow data recording templates to be available to the pharmacies online so that they can enter the data at the time of the consultation, and the data will go directly to the database. It also allows the research team to have access to live and comprehensive data. The CTU will ensure full GDPR compliance and that all data is stored in secure cloud access in the UK. They will assist with participant information sheets, consent forms and applying for ethical approval. The CTU will also conduct all randomisation and statistical analysis, and provide data monitoring and study support. GL and the LinCTU will play a significant role in the final evaluation of feasibility.

**Study Steering Group**. The Study Steering Group will meet every six months to ensure all practical details of the study are progressing well and to ensure adherence to timescales and reporting to NIHR.

**Patient and Public Involvement and Engagement (PPIE) Panel**. The PPIE panel will meet bi-monthly to ensure the study remains sensitive to patient and public preferences at all stages. Specifically, they will be involved in reviewing all study participant and public facing materials, co-developing the response service and evaluation of the main findings.

**Study Management Group**. The Study Management Group consists of the research team, co-investigators and relevant local partners. They will meet bi-monthly to discuss the progress of the study and discuss the findings as they emerge.

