#### SECONDARY ENDPOINTS/OUTCOMES

Secondary outcome measures are (i) subsequent management and referrals to support organisations (ii) client quality of life (based on EQ5D) (iii) acceptability of the service to clients (iv) client demographics (v) cost and economic considerations of the service.

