# **B. Co-development**

# 1. One-to-one scoping interviews with key stakeholders

A minimum of 8 scoping interviews will be held with representatives of relevant referral organisations (for example – Women's Aid, Samaritans, Emergency Department, Mental Health Crisis Team, Adult Social Care Domestic Abuse Co-ordinator, the Police, Addaction (now known as "We are with you")). They will be recruited via targeted e-mails followed up with a participant information sheet and consent form. In-depth semi-structured interviews will be conducted, using scenarios to map and ascertain appropriate referral and support pathways for different levels of severity and urgency for suicidal ideation or domestic abuse (and any accompanying alcohol or substance misuse), and appropriate content of an education and training resource for pharmacy staff delivering the intervention. Views will also be sought on requirements for appropriate mentoring of pharmacy staff in case of distress during the study, on the requirements for clinical record keeping and on the content of the client self-report evaluation questionnaire (to be used in the evaluation). Interviews will be recorded and transcribed. Data will be analysed using framework analysis. Recruitment and interviewing will continue until consensus and data saturation are achieved. These interviews will contribute to the development of the triage and referral tool. This will be an iterative process to create and embed appropriate referral pathways.

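### Client acceptability and satisfaction are gathered by the staff delivering the service, with no route for an answer those staff do not see

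*Protocol*

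**What the plan says.** The Protocol lists "iii) acceptability of the service to clients" among its secondary outcomes. The primary objective asks how feasible and acceptable the service is, and objective 5 names client views first among those to be ascertained.

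The section on collecting data from service users at the time of access (Ethical and Regulatory Considerations, Phase 2, 1.C) describes how those views are obtained:

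- Who asks: "The pharmacy staff will explain this is a trial service and invite the individual to offer their views".
- When: "The data will be collected during the consultation".
- Scope: "In terms of data collection, all of the client data is collected in the consultation".
- Content: "It will comprise of simple demographic data, brief views about acceptability, satisfaction and health status".

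Study Management Committees describes online templates for the pharmacies, "so that they can enter the data at the time of the consultation, and the data will go directly to the database". The usage and referral data section adds brief acceptability items to what is collected after triage. The schedule of procedures places satisfaction at intervention delivery only.

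One other section describes a different instrument. The Phase 1 stakeholder interviews are to seek views on "the content of the client self-report evaluation questionnaire (to be used in the evaluation").

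**The concern.** The client gives an opinion of the service to the person who has just provided it, in the same room, and the pharmacy enters the answer. Section C itself expects many clients to be distressed. People in that position may soften or withhold criticism, so the recorded answers may look better than the views actually held.

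What is at stake is secondary outcome (iii), the client part of objective 5 and the acceptability half of the primary objective. A feasibility study exists largely to find out whether the service is acceptable. Appendix 1 (item 35) also asks whether acceptability and satisfaction could be measured in a future trial. A method prone to favourable answers gives weak information on both.

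The mention of a self-report questionnaire adds a second difficulty: a reader cannot tell which mode of completion is planned.

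**Working it through.** The plan states no figure for client acceptability or satisfaction, so there is none to reproduce. The check sets the sections side by side.

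1. **Is there a return the provider does not see?** Section C, the usage and referral data section, the CTU paragraph and the schedule were compared. All place collection within the consultation or service delivery, and data entry is by the pharmacies. None mentions self-completion, a sealed return or an independent collector.

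2. **Does another source supply direct client views?**
 - Customer interviews: the Phase 2 exclusion criteria bar those who have used the service, and the interview sections repeat that they are for general customers.
 - Later contact: section C rules it out, for confidentiality and safety.
 - E-survey: the exclusions are age and residence only, and distribution includes the intervention pharmacies, so a service user could respond. Nothing says that service users will be identified as such.
 - Appendix 1, criterion 15 (client experience): the sources are monthly visits, mentoring and staff focus groups, so it too reaches the study through staff.

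 The consultation data are therefore the main direct client evidence.

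3. **Who is asked?** Section C has staff invite clients triaged at Levels 1 and 2, and lets them omit the supplementary research data (Part B) in cases of considerable distress or urgency. The provider thus also influences whose views are recorded. That is justified on welfare grounds, but it is a further reason to read the results with care.

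4. **Is the mode consistent?** The stakeholder-interview section speaks of a client self-report questionnaire for use in the evaluation. The usage and referral data section treats completing a questionnaire as something to ask clients about for a future trial. The schedule lists no questionnaire. Section C describes staff inviting views. These have not been reconciled.

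5. **Direction and size.** Suppose a true share *d* of clients is dissatisfied and a share *m* of them does not say so to the provider. Recorded dissatisfaction is then *d* × (1 − *m*). Purely as an illustration, with *d* = 0.30 assumed:
 - *m* = 0: 0.30 × 1.0 = 30%, no bias
 - *m* = 0.3: 0.30 × 0.7 = 21%
 - *m* = 0.5: 0.30 × 0.5 = 15%
 - *m* = 0.7: 0.30 × 0.3 = 9%

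 Neither *d* nor *m* comes from the documents, and *m* could not be estimated from data collected in a single mode. The lines show direction only.

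**The case against.** The collection setting is a reasoned choice that the Protocol discloses. Section C weighs data needs against burden, gives a safety reason for no later contact, tells clients that declining will not affect their care and that research data are anonymised, and cites public involvement in the design. It also expects Phase 1 to refine the data collection tools. All of this stands. It justifies collecting on site, but it does not require the providing staff to see the answers, and anonymised storage does not hide an answer from the person in the room.

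Several stronger readings are tempting and are not supported:

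- *The sections contradict each other.* Section C fixes when data are collected and who invites views. It does not say that staff read the items aloud or score them. A form filled in by the client during the consultation would fit both it and the stakeholder-interview section. This is an unreconciled inconsistency.
- *The economic section promises a self-report satisfaction form.* It says "We will collect resource use and outcome data using a self-reporting questionnaire", but this concerns inputs to the economic model and does not mention satisfaction.
- *The measure cannot show unacceptability, or will certainly be biased.* Some dissatisfaction would still be recorded unless every dissatisfied client stayed silent. The documents support a risk of bias and no more.
- *It is the only client evidence.* The e-survey does not bar service users, and previous use, reasons for choosing the service and willingness to be followed up are indirect signals.
- *A progression decision rests on it.* Appendix 1 sets no threshold for client-rated acceptability or satisfaction.
- *The client depends on the staff member for a referral when asked.* The items follow triage, but their order relative to the referral is not stated.

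**Conclusion.** The point holds as a risk of bias in one secondary outcome, together with an inconsistency in the text. Client acceptability and satisfaction are invited by the providing staff and entered by the pharmacy during the consultation, with no return unseen by them, and no other planned source gives identifiable direct client views. The expected direction is towards acceptable. That rests on the general assumption that some clients are less candid with the person who has just helped them. The size cannot be derived from the documents.

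The consequence falls on secondary outcome (iii), objective 5 and the acceptability part of the primary objective. It does not touch the primary outcome, which is the number of consultations, or any red/amber/green cut-off. This is a cheap improvement to the design and does not invalidate the study.

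**What to change.** Reconcile the stakeholder-interview section, the usage and referral data section, section C and the schedule of procedures so that they describe one mode:

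- Where the client is able, the brief acceptability and satisfaction items are self-completed on site before leaving and returned unseen by the providing staff, on a slip placed in a sealed box or on a screen that staff do not view.
- Staff may remain present, so the client need not be left alone. No later contact is involved, and the existing discretion to omit Part B is unchanged.
- Where self-completion is not possible, staff may ask the items. The mode is recorded for every client, and staff-asked answers are reported separately.
- The schedule lists the form.

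The cost is a printed slip and box or one extra screen, a slightly longer consultation and some additional non-response. There is also a small translation cost: the Inclusivity section costs translated information sheets and translators for customer interviews, but not a client form.
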